9.4.3 ANALYSIS OF THE SECONDARY ENDPOINT(S)

For each secondary endpoint:

A Generalized Estimation Equation (GEE) Model, including baseline records, will be used to check for changes in LEFS, FACES pain scale, and Godin Leisure-Time Exercise between treatment groups over time. Results for LEFS and Godin Leisure-Time Exercise will be presented as mean with 95% confidence interval, and results for FACES pain scale will be reported as odds ratio and 95% confidence interval.

9.4.4 SAFETY ANALYSES

A GEE model will be conducted to estimate likelihood of occurring and intensity of adverse events for Pediatric patients with apophysitis of the knee who receive iontophoresis with DSP treatment and PT as compared to those who receive placebo or PT alone.

9.4.5 BASELINE DESCRIPTIVE STATISTICS

Age at admission and baseline patient reported outcomes will be compared between treatment groups using Analysis of Variance (ANOVA) test. Chi-square test will be conducted to test comparability of intervention groups in terms of gender and race distribution. Continuous variables will be presented as mean and standard deviation. Categorical variables will be expressed as frequency and percentage. All tests will be two-sided and p < 0.05 will be considered statistically significant.

9.4.6 SUB-GROUP ANALYSES

A Generalized Linear Model (GLM), including concomitant therapies, age, gender, and race will be conducted to analyze the possible effect of these covariates on length of time to RTS outcomes.

Generalized Estimation Equation model including concomitant therapies, age, gender, and race will be conducted to assess the effect of these covariates on LEFS, FACES, Godin Leisure-Time Exercise, and safety outcomes.

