6.5 CONCOMITANT THERAPY

Concomitant therapy during this study to include:

- NSAIDs for pain as recommended by referring physician, if applicable
- Brace use as recommended by referring physician, if applicable
- Ice for pain per standard of care as described on handout provided to all patients

Patients and/or parents will be asked at the beginning of each PT treatment about use of the concomitant treatment options listed above. This will be documented by the treating physical therapist each visit. Each of these concomitant treatments may help reduce pain, but they will be recommended to participants across all three treatment groups, so it is feasible to analyze and distinguish independent effects of the study intervention compared to any potential effects from the concomitant therapies described above.

For this protocol, a prescription medication is defined as a medication that can be prescribed only by a properly authorized/licensed clinician. Medications to be reported in the Case Report Form (CRF) are concomitant prescription medications, over-the-counter medications and supplements.

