8.2 SAFETY AND OTHER ASSESSMENTS

The following procedures/evaluations will be obtained by qualified Therapists treating the subjects: Assessed At Enrollment/Randomization Study Treatment Visit 1:

 Inclusion/Exclusion Criteria - Based on the patient's medical history and review of the initial evaluation, the Treating Therapists will determine whether patients meet eligibility criteria for the study.

Note: if radiograph images were obtained to determine skeletal maturity, the Treating Therapist will ensure the results are documented in the radiologist's notes or noted in the physician's notes in the electronic medical record.

- Informed Consent Treating Therapist will conduct the informed consent process as outlined in Section 10.1.1.2 of this document.
- Randomization After a patient signs Consent, the Treating Therapist will assign the patient to the research group per the randomization log at the Site (see section 6.3 Measures to Minimize Bias: Randomization and Blinding).

Assessed at All Study Treatment Visits:

- Brief Physical examination of the affected knee an evaluation made by the treating physical therapist to include: skin color, temperature, presence of edema, turgor, pain with palpation/pressure, changes to skin texture, and integrity. Also assessed at Clinic Check visit.
- Concomitant Medication Review a paper-based form completed by the Treating Therapist to document drug, dose, frequency, start and stop dates, and reason for taking. Also assessed at Clinic Visit Check visit.
- Adverse Event Evaluation a paper-based form completed by the Treating Therapist to document occurrence, severity, relatedness, duration, and expectedness of the event. Subjects receiving iontophoresis will be specifically monitored for possible burns. This data will be captured during the examination of the affected knee as well as for 15 minutes post patch application.

Also assessed at Clinic Visit Check visit, 30-Day Phone Follow Up and electronically at the 90-Day Follow Up (see Appendix 12.6 90-Day Follow Up – Electronic Survey)

• Compliance Checks – a paper-based form completed by the Treating Therapist to assess participant compliance with: study visits, length of time iontophoresis patch worn, home exercise program, icing, activity restriction, and bracing instructions. Also assessed at Clinic Check visit.

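### The supportive models in 9.4.6 include concomitant therapy that is recorded mainly after randomisation, and 6.5 wrongly treats equal recommendation as enough to isolate an independent treatment effect

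*Combined protocol and SAP*

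**What the plan says.** Section 9.4.6 plans a covariate model for the primary endpoint: "A Generalized Linear Model (GLM), including concomitant therapies, age, gender, and race will be conducted to analyze the possible effect of these covariates" on time to RTS. For the other outcomes it says: "Generalized Estimation Equation model including concomitant therapies, age, gender, and race will be conducted to assess the effect of these covariates on LEFS, FACES", and goes on to list Godin and safety. Section 4.1 repeats the plan for time to RTS. Neither section states a treatment term, or the timing or coding of the concomitant-therapy variable.

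Section 6.5 defines the therapies as those used during the study: NSAIDs ("NSAIDs for pain as recommended by referring physician, if applicable"), brace as recommended by the referring physician, and ice for pain. Patients or parents are "asked at the beginning of each PT treatment about use of the concomitant treatment options listed above", and the therapist documents the answer each visit. The section grants that each therapy could ease pain, notes that every arm gets the same recommendations, and concludes: "so it is feasible to analyze and distinguish independent effects of the study intervention compared to any potential effects from the concomitant therapies".

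Randomisation takes place at Study Treatment Visit 1 (section 8.2): "After a patient signs Consent, the Treating Therapist will assign the patient to the research group per the randomization log".

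The treatment comparisons in 9.4.2 (primary), 9.4.3 (secondary) and 9.4.4 (safety) list no concomitant-therapy covariate.

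**The concern.** The argument in 6.5 rests on recommendation being the same in all arms. What is recorded each visit, and would naturally be analysed, is use, and randomisation does not balance use once treatment has begun. The documents themselves show three ways in which use can depend on arm or outcome:

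- NSAIDs and ice are used for pain, which the study drug is meant to reduce. (Section 6.5 does not say this of the brace.)
- The PT-alone arm is unblinded (4.2, 6.3), so those families may use these measures differently.
- Use is logged per visit and study treatment ends when RTS criteria are met (7.1). If the variable is coded as cumulative use or ever-use, slow recovery itself produces more recorded use.

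In the safety model an NSAID started because of an adverse event would be a consequence of the outcome; the 30-day form in Appendix 12.5 anticipates new medication for that reason.

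At stake is how the supportive results are read. A treatment coefficient adjusted for on-study use is not the total effect. Nor is it a clean direct effect if severity drives both use and recovery. Section 6.5 invites readers to call it an independent effect. The covariate effects, which are the stated aim of 9.4.6, have the same problem: children in more pain use more and recover later.

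**Working it through.** **The plan's own figure.** Section 9.2 gives N = 126 for f = 0.28, 80% power and alpha 0.05. For a three-group F test with df 2 and 123, noncentrality is f²N = 0.28² × 126 = 9.88 and power is 0.8002, so 126 reproduces. The rest of this point does not alter it.

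**Timing.** The Schedule of Activities has up to 12 study treatment visits plus a Clinic Check. At most one of those records, at Visit 1, precedes the first study treatment.

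**Size, first illustration (two arms, all values assumed).** The documents give no usage rates and no effect of treatment on use. In SD units of time to RTS, with T = 1 for DSP:

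- pain = −0.6T + U, with U standard normal
- use = 1 if r·pain + √(1−r²)·e > 0, otherwise 0
- time = 0.8·pain − c·use + 0.6·noise, where c is the benefit of use

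The effect through pain is 0.8 × (−0.6) = −0.48. Use is p0 = 0.5 in controls and p1 = Φ(−0.6r) on DSP; let Δ = p0 − p1. The within-arm slope of time on use, before any real benefit of use, is

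g = 0.8·r·[φ(0) + φ(0.6r)] / [p0(1−p0) + p1(1−p1)].

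Then:

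- total effect = −0.48 + cΔ
- effect adjusted for use = −0.48 + gΔ
- bias = (g − c)Δ
- coefficient for use = g − c, against a true value of −c

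For r = 0.5: p1 = Φ(−0.30) = 0.382 and Δ = 0.118. So g = 0.4 × (0.3989 + 0.3814)/(0.2500 + 0.2361) = 0.642, and the adjusted effect is −0.48 + 0.642 × 0.118 = −0.404.

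| r | Δ | g | Adjusted | Total, c = 0 | Total, c = 0.3 | Total, c = 0.6 | Adjusted against total (c = 0; 0.3; 0.6) |
|---|---|---|---|---|---|---|---|
| 0.3 | 0.071 | 0.384 | −0.453 | −0.480 | −0.459 | −0.437 | 6% smaller; 1% smaller; 4% larger |
| 0.5 | 0.118 | 0.642 | −0.404 | −0.480 | −0.445 | −0.409 | 16%; 9%; 1% smaller |
| 0.7 | 0.163 | 0.904 | −0.333 | −0.480 | −0.431 | −0.382 | 31%; 23%; 13% smaller |

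A simulation of the same model agrees with these values. If Δ = 0 the bias is zero. The coefficient for use is off by g in every row. With c = 0.3, a true benefit of −0.30 would be estimated as +0.08, +0.34 or +0.60, which is the wrong sign.

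**Size, second illustration (three arms, 42 per arm, 4,000 simulated trials).** f = 0.28 with DSP against two equal controls is d = 0.28 × 3/√2 = 0.594 SD. An unmeasured severity variable affects both use and time to RTS.

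| Assumption | Adjusted effect (true −0.594) | Power, unadjusted to adjusted |
|---|---|---|
| Treatment does not change use | −0.594 | 0.81 to 0.82 |
| Lowers use 0.3 SD; severity paths 0.5 and 0.5 | −0.523 (12% smaller) | 0.80 to 0.70 |
| Lowers use 0.6 SD; paths 0.5 and 0.5 | −0.451 (24% smaller) | 0.81 to 0.53 |
| Lowers use 0.6 SD; paths 0.3 and 0.3 | −0.541 (9% smaller) | 0.80 to 0.68 |
| Lowers use 0.3 SD; paths 0.5 and 0.5; use also shortens recovery | −0.580 (2% smaller) | 0.80 to 0.77 |

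With no true treatment effect but an effect on use, the adjusted estimate is +0.05 to +0.15 SD and type I error is 0.05 to 0.10.

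**Cost of baseline covariates.** At N = 126 and f = 0.28, spending six degrees of freedom on baseline covariates moves power from 0.8002 to 0.7997.

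**The case against.** The strongest reply is that 9.4.6 does not set out to estimate a treatment effect. It sits under sub-group analyses, states its aim as the effect of the covariates, and names no treatment term. Section 6.5 names no model and does not refer to 9.4.6. This stands. A reader might infer that the plan will report a biased independent treatment effect, but the documents do not say that such an estimate will be reported. The link remains reasonable: 9.4.6 is the only planned analysis containing concomitant therapy, so it is the only one that could deliver what 6.5 claims. If treatment is left out of the models, that claim has no supporting analysis.

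Second, the covariate is undefined. NSAID and brace use follow the referring physician's recommendation, and 5.3 and 8.1 place these instructions in standard care and the Initial Evaluation. A yes/no code for recommendation could be fixed before randomisation and would do no harm. This stands as a possibility, but 6.5 speaks of use during the study, asked about every visit, which makes on-study use the natural reading.

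Third, a reader might infer that adjustment must understate the effect. It need not. Understatement by 6% to 31% requires that use has no effect on recovery, whereas 6.5 says these therapies may reduce pain. Allowing for a benefit shrinks the bias and can reverse it.

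**Conclusion.** The point holds for the supportive models. The inference in 6.5 from equal recommendation to separable effects is not valid, and the natural reading of 9.4.6 puts a variable that treatment can change into the models. If on-study use enters with a treatment term, the treatment coefficient can be biased for the total effect. With or without that term, the effect of use is confounded by severity.

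Size and direction cannot be derived from the documents. Across the assumed values the adjusted effect runs from about 4% larger to about 31% smaller than the total effect, with no bias from this source if treatment does not change use. These figures illustrate the range and do not predict this trial's result.

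The stronger reading, that the trial's treatment conclusions are compromised, is not supported: 9.4.2 to 9.4.4 list no such covariate, nothing lets the 9.4.6 models replace those analyses, and N = 126 is unaffected. The change is still worth making, because an undefined covariate lets baseline, ever-use, cumulative or per-visit coding be chosen after the data are seen.

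**What to change.** In 9.4.6 (and 4.1):

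- Define the concomitant-therapy covariate as use recorded at Visit 1 for a period ending before randomisation, or at the latest before the first study treatment. Take NSAIDs from the medication review, and ice and brace from the compliance check or the Visit 1 questions in 6.5. State the coding.
- State that treatment inference rests on the models without on-study use.
- Tabulate on-study use by arm as a descriptive outcome.
- Label any model containing on-study use as exploratory, and do not describe its treatment coefficient as an independent effect.

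In 6.5, delete the claim that independent effects can be distinguished.

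The cost is wording; the Visit 1 items are already scheduled and the power loss is negligible. There are two small downsides. Prior use may be sparse for children whose Initial Evaluation, where the instructions are given, falls on the same day as Visit 1. A baseline covariate also says nothing about the effect of on-study use, which these data could not estimate without further assumptions.

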9.4.7 INTERIM ANALYSES

While recruitment is ongoing, interim results will be supplied, in strict confidence, to the ISM as frequently as requested. All individuals involved in the interim analyses, including the biostatistician, will be blinded to intervention assignment.

Interim analysis of the study will be conducted based on the alpha spending rule .²⁶ The proportion of the observed sample size (number of patients observed divided by the target sample size) will be considered as the information statistics. The p-value will be adjusted to maintain the overall study power of 0.05, two-sided.

The ISM will inform the PI of the results only if the test statistics exceeds the adjusted p-value in the primary efficacy or safety outcome and if, in the opinion of the ISM, the study should be considered for early termination. The study would not be terminated early if the difference is found only in a secondary outcome of efficacy, the p-value is smaller but close to the adjusted p-value, or when the variance is small. The decision to terminate the study early would be made by the ISM with consultation of a non-treating physician as needed.

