8.3.5 ADVERSE EVENT REPORTING

The Treating Therapist will record all adverse events on an Adverse Event Log and will evaluate for seriousness, severity, expectedness, and relatedness. Adverse events that impact the safety of the subject or the ability of the subject to continue on with the study will be communicated immediately (within 24 hours) to the referring physician. On a monthly basis, the Principal Investigator will provide the Independent Safety Monitor cumulative AE reports. The Independent Safety Monitor, in consultation with a physician as needed, will monitor for accuracy and will have the authority to recommend continuation of the trial, modification to the trial, or termination of the trial in the event of unacceptable adverse events.

The Sponsor will notify all participating Investigators and the FDA (via an IND Safety Report) of any potential serious risks as soon as possible, but no later than 15 calendar days after the Sponsor determines that the information qualifies for reporting. Any adverse event not initially determined to be reportable but later determined to be reportable, will be submitted as an IND Safety report to the FDA as soon as possible, but no later than 15 calendar days after the determination is made.

EVENT	REPORTED BY WHOM	TO WHOM (TIMEFRAME TO
		REPORT)
AE deemed Serious – see Section 8	3.3.6 Serious Adverse Event Reportion	ng
AE deemed Not Serious	Treating Therapist	 Principal Investigator (provide
		in weekly AE Report)
	Principal Investigator	 Independent Safety Monitor
		(ISM) (provide in monthly AE
		Report)
AE deemed Severe	Treating Therapist	 Principal Investigator –
		Immediately (within 24 hours
		of becoming aware of event)
	Principal Investigator	 Referring Physician –

The following AE reporting guidelines will be utilized in this protocol:

		 immediately (within 24 hours of becoming aware of event) ISM - Immediately (within 24 hours of becoming aware of event)
AE deemed Related	Treating Therapist	 Principal Investigator (provide in weekly AE Report)
	Principal Investigator	 ISM (provide in weekly AE Report)
AE deemed Unexpected	Treating Therapist	 Principal Investigator – Immediately (within 24 hours of becoming aware of event) Referring Physician – immediately (within 24 hours of becoming aware of event)
	Principal Investigator	 1. ISM - Immediately (within 24 hours of becoming aware of event)

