10.1.5 SAFETY OVERSIGHT

Safety oversight will be under the direction of an ISM, an individual with the education, skills, and relevant expertise whose primary responsibility is to provide independent safety monitoring in a timely fashion. This is accomplished by review of adverse events with follow-up through resolution. The ISM, in consultation with a physician as needed, will evaluate individual and cumulative participant data when making recommendations regarding the continuation of the trial, modification to the trial, or termination of the trial in the event of unacceptable adverse events.

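### Section 9.4.7 ties disclosure of between-arm interim safety results, and stopping on them, to an alpha-spending p-value, and is not reconciled with the threshold-free safety authority in 8.3.5, 10.1.2 and 10.1.5

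*Combined protocol and SAP*

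**What the plan says.** Section 9.4.7 (Interim Analyses) sets one statistical rule: "Interim analysis of the study will be conducted based on the alpha spending rule", with information measured as patients observed over the target sample size. On the adjustment it says: "The p-value will be adjusted to maintain the overall study power of 0.05, two-sided". I read the word power there as type I error. It gives no spending function, no number or timing of looks, and no separate boundary for harm.

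Disclosure has two joined conditions. The first is statistical: the monitor "will inform the PI of the results only if the test statistics exceeds the adjusted p-value in the primary efficacy or safety outcome". A crossing in either primary efficacy or safety meets it. The second is the ISM's own judgment: "and if, in the opinion of the ISM, the study should be considered for early termination".

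The section then lists situations in which the study would not stop early. One is a difference confined to a secondary efficacy outcome. The other two are: "the p-value is smaller but close to the adjusted p-value, or when the variance is small". Neither of these is restricted to efficacy. The decision to terminate is left to the ISM, with a non-treating physician consulted as needed.

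Three other sections carry no p-value condition:

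- **8.3.5 (Adverse Event Reporting):** the ISM "will have the authority to recommend continuation of the trial, modification to the trial, or termination of the trial" where adverse events are unacceptable.
- **10.1.5 (Safety Oversight):** the ISM weighs individual and cumulative data in recommending, among other things, "termination of the trial in the event of unacceptable adverse events".
- **10.1.2 (Study Discontinuation and Closure):** unacceptable risk is listed as a ground for suspension or termination.

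**The concern.** Alpha spending guards against a false claim of benefit from repeated looks. Applied to harm, it raises the evidence needed before anyone outside the interim review may be told, and it is strictest at early looks. As 9.4.7 is worded, an ISM worried by a between-arm imbalance has no permission to share the comparison until the threshold is crossed. If it is crossed narrowly, the section says the trial continues. The terms close and small are not defined.

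This matters because the participants are children, the route of administration is not FDA-approved, and section 2.3.1.2 says there are no published data on systemic effects by this route. Individual reports may not reveal an excess of mild or moderate expected skin reactions. Such an excess shows mainly when arms are compared, and that comparison is what 9.4.7 restricts.

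**Working it through.** **Passages side by side**

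| Question | 9.4.7 | 8.3.5, 10.1.2, 10.1.5 |
|---|---|---|
| What triggers action on safety? | Adjusted p-value crossed, plus ISM opinion | Unacceptable adverse events or risk |
| Is a significance threshold needed? | Yes, the same one as for efficacy | No |
| What if the crossing is narrow or the variance small? | No early termination | Not mentioned |
| Does it refer to the other rule? | No | No |

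Section 10.3 records that interim-analysis language came in with version 6.0. It gives no order of precedence.

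**What the PI already knows.** Under 8.3.5 and 8.3.6, therapists send severe, serious and unexpected events to the PI within 24 hours, and related and non-serious events weekly. The PI compiles the monthly cumulative report for the ISM. The events are therefore known to the PI. Pharmacy holds the randomization key (6.3), and the documents do not say that the PI's reports identify the DSP (dexamethasone sodium phosphate) arm.

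**Illustration of the threshold.** Section 9.4.7 states no boundary, so there is no figure of the plan's to reproduce. The only inputs from the plan are 49 per group (9.2) and two-sided 0.05. These are assumed: a first look at information t = 0.5, about 24 per arm (49/2 = 24.5), and a two-sided Fisher exact test on children with at least one event. Section 9.4.4 itself specifies a GEE model.

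At a first look the threshold equals the alpha spent:

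- O'Brien-Fleming type, 0.025 on each side: 4[1 − Φ(2.241/√0.5)] = 4[1 − Φ(3.170)] = 0.0031
- The same form applied to two-sided 0.05: 2[1 − Φ(1.960/√0.5)] = 2[1 − Φ(2.772)] = 0.0056
- Pocock type: 0.05 × ln(1 + (e − 1) × 0.5) = 0.0310

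For k DSP children with events against 0 of 24, p = 2·C(24,k)/C(48,k):

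- k = 5: 0.0496
- k = 6: 0.0219
- k = 7: 0.0094
- k = 8: 0.0039
- k = 9: 0.0016

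Against 0 of 48 (placebo and PT alone pooled), p = C(24,k)/C(72,k) for the values used here:

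- k = 3: 0.0339
- k = 4: 0.0103
- k = 5: 0.0030

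Smallest number of DSP children, out of 24, that crosses:

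| Threshold | vs 0/24 | vs 1/24 | vs 0/48 | vs 1/48 |
|---|---|---|---|---|
| 0.0310 | 6 | 8 | 4 | 5 |
| 0.0056 | 8 | 10 | 5 | 6 |
| 0.0031 | 9 | 11 | 5 | 7 |

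The 5 in the last row is on the edge (0.00304 against 0.00305). With t taken as exactly 24/49 the threshold is 0.0027 and 6 are needed.

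If true event rates were 20% on DSP and 2% on placebo (assumed), the chance of crossing at this look in the DSP-versus-placebo comparison is about 24%, 6% and 2% for the three thresholds in table order.

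**The case against.** The strongest reply is that the sections differ in scope. Section 9.4.7 governs the results of the interim statistical analysis, while 8.3.5 and 10.1.5 govern adverse event review. Neither of those, nor 10.1.2, is made subject to 9.4.7. That reading is available, and under it the ISM can act on adverse events without any p-value. It does not settle what happens when the ISM's concern comes from the interim comparison itself, nor whether the two unrestricted exceptions bind a safety decision.

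A reader might infer that clear harm could go undisclosed, or that 9.4.7 overrides the other sections because it was added later. The documents support neither. Events reach the PI weekly or within 24 hours, Group C is unblinded, therapists know whether a child receives bottle A or B, and the threshold-free authority remains in the same protocol version. Nor does a safety p-value alone control disclosure: an efficacy crossing can also open it, and the ISM's opinion is always required as well.

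The size is also open to challenge, and rightly. The test, look time, spending function and comparator are all assumed, so no single count is a property of this plan. Burns are a risk of iontophoresis in both patch arms, so DSP versus placebo would say little about them. Section 2.3.3 also reports over 23,000 such treatments at this program with no significant adverse reaction. That lowers the expected stakes but does not tell the ISM which rule to follow.

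**Conclusion.** The point holds as an unreconciled conflict that should be corrected. Section 9.4.7 puts between-arm safety results behind the efficacy threshold. Read literally, it also bars stopping on a narrow safety crossing, while three other sections let safety action proceed with no threshold, and no order of precedence is given. What can be withheld is the comparative interim result, not the adverse events.

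Under the assumptions shown, crossing needs about 6 to 9 of 24 DSP children affected against 0 of 24 on placebo, or about 4 to 5 of 24 against 0 of 48 pooled controls. The range shows that a sizeable imbalance can miss the threshold. It does not predict how this trial's interim analysis would behave. The textual conflict does not depend on these figures.

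**What to change.** Reconcile the passages in 9.4.7:

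1. Confine the adjusted p-value, the condition on informing the PI, and the narrow-crossing and small-variance exceptions to the primary efficacy outcome.
2. State that 9.4.7 does not limit the ISM's authority under 8.3.5, 10.1.2 and 10.1.5. At any look, without a significance threshold, the ISM may communicate safety concerns, including between-arm imbalances, and recommend modification, suspension or termination.

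The cost is about two sentences in an amendment. The efficacy type I error is not inflated, because stopping for harm makes no claim of benefit. No change to the sample size or data collection is needed.

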9.2 SAMPLE SIZE DETERMINATION

To assess the primary variable of interest, a power analysis indicated that a total sample of 126 participants would be required to detect medium effects (f = 0.28) with 80% power and $\alpha = 0.05$ using Generalized Linear Model (GLM).

The required sample size to test secondary hypotheses was calculated as 87 and 108 participants for patient reported outcomes and safety, respectively. Therefore, a total sample of 126 participants provides sufficient power for testing secondary hypotheses.

Given an estimated 15% non-compliance rate, the sample size will be increased by 15%, for a total sample size of 147 participants (49 per group).

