9.4 STATISTICAL ANALYSES

9.4.1 GENERAL APPROACH

Continuous variables will be expressed as mean, standard deviation, median, and range. Categorical variables will be presented as frequency and percentage. All statistical tests will be two-sided and p < 0.05 will be considered as statistically significant.

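### Section 9.4.7 mis-states its interim stopping rule, and section 9.4.1 conflicts with it on the level of the final primary test

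*Combined protocol and SAP*

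**What the plan says.** Section 9.4.7 (Interim Analyses) states: "Interim analysis of the study will be conducted based on the alpha spending rule", with a general citation to the alpha spending approach. Information is the "number of patients observed divided by the target sample size". The level is set by this sentence: "The p-value will be adjusted to maintain the overall study power of 0.05, two-sided". Results go from the Independent Safety Monitor (ISM) to the principal investigator "only if the test statistics exceeds the adjusted p-value in the primary efficacy or safety outcome", and only if the ISM also thinks early termination should be considered. The section then lists cases in which the trial would not stop, among them when "the p-value is smaller but close to the adjusted p-value, or when the variance is small".

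Section 9.4.1 (General Approach) states: "All statistical tests will be two-sided and p < 0.05 will be considered as statistically significant". Section 9.4.2, on the primary analysis, gives no other level for the final test.

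Section 9.2 sets alpha at 0.05 and power at 80%, and finds that "a total sample of 126 participants would be required to detect medium effects" (f = 0.28). It then raises the total to 147. The amendment history (section 10.3) shows that the interim language came in with version 6.0.

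**The concern.** Three things in these sections do not fit together.

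- **The quantity held at 0.05.** Section 9.4.7 calls it power. Section 9.2 plans 80% power and alpha of 0.05, so type I error must be meant.
- **The trigger.** A test statistic cannot be compared with a p-value. If the sentence is read as a p-value exceeding its bound, the direction is reversed, and the following sentence, which treats a smaller p-value as the crossing, contradicts it.
- **The final test.** Alpha spent at interim looks has to be taken from the final test. Section 9.4.1 sets 0.05 for all tests, and nothing there or in section 9.4.2 points to section 9.4.7.

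A secondary point is that no spending function is named. Alpha spending is a family of rules, so the interim bound cannot be computed from the text.

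At stake are the rule for disclosing interim results and considering early termination, and the level of the test that decides the primary endpoint. Two statisticians working from the same text could reach different bounds and different final levels.

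**Working it through.** **Inputs.** From section 9.2: alpha = 0.05 two-sided, power 80%, f = 0.28, N = 126 before inflation and 147 after. From the design: three equal arms. Assumed, because the plan gives none: the spending function, and one to four equally spaced interim looks.

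**1. The plan's own sample size.** One-way F test on 2 and N - 3 degrees of freedom, noncentrality N × f². At N = 126 this is 126 × 0.28² = 9.88 and power is 0.8002, so 126 reproduces (123 gives 0.790). For the inflation, 126 × 1.15 = 144.9, and the next multiple of three above that is 147. Neither figure allows for interim looks.

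**2. Bound at a first look, t = 0.5.** At a first look the nominal p bound equals the alpha spent.

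- O'Brien-Fleming-type, 0.025 per side: 4[1 - Φ(2.2414/√0.5)] = 0.0031.
- O'Brien-Fleming-type, 0.05 entered directly: 2[1 - Φ(1.960/√0.5)] = 0.0056.
- Pocock-type: 0.05 × ln[1 + (e - 1) × 0.5] = 0.031.

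The first and last differ tenfold. An interim p-value of 0.02 would cross under Pocock-type spending and not under either of the others.

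**3. Overall error if the final test is run at 0.05 after spending at the interims.** Recursive numerical integration, for a 1-df contrast and for the 2-df three-arm test:

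| Spending | df | 1 interim | 2 | 3 | 4 |
|---|---|---|---|---|---|
| O'Brien-Fleming-type, 0.025 per side | 1 | 5.10% | 5.35% | 5.54% | 5.66% |
| | 2 | 5.11% | 5.39% | 5.59% | 5.72% |
| O'Brien-Fleming-type, 0.05 direct | 1 | 5.22% | 5.56% | 5.77% | 5.90% |
| | 2 | 5.24% | 5.61% | 5.83% | 5.97% |
| Pocock-type | 1 | 6.86% | 7.22% | 7.37% | 7.44% |
| | 2 | 6.94% | 7.31% | 7.46% | 7.54% |

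If the final bound is computed from the alpha that remains, the error is 5.0% in every row.

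**4. Final level left by spending.** With looks at 49 and 98 of 147 (t = 1/3 and 2/3), the nominal p bounds for O'Brien-Fleming-type spending at 0.025 per side are 0.0002, 0.0120 and 0.0463 for 1 df, or 0.0002, 0.0120 and 0.0459 for 2 df.

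**5. Power at the reduced final level.** Same F test, fixed sample, before crediting early rejections:

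| N | at 0.05 | at 0.0463 | at 0.0459 |
|---|---|---|---|
| 126 | 80.0% | 79.1% | 79.0% |
| 147 | 86.2% | 85.5% | 85.4% |

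**The case against.** The strongest defence is that section 9.4.7 already governs the final test. It commits to keeping an overall 0.05, which cannot be done unless the final test is included. It is also the more specific and later text, so section 9.4.1 may simply not have been updated. On that reading the error is 5.0%, and the documents do not instruct anyone to exceed it. Most of this stands. What remains is that the commitment appears under interim analyses and gives no final level, while section 9.4.1 covers all tests without qualification.

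The two wording faults can also be resolved from context: section 9.2 settles what 0.05 means, and the sentence on a smaller p-value settles the direction. They should still be corrected, because they stand in the operative rule.

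A reader might infer more than the documents support:

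- *That looks on request inflate the error by themselves.* Testing at 0.05 at every look would give about 8.3%, 10.8% and 12.7% after one, two and three equally spaced interims (1 df). The plan does not say this. It commits to alpha spending, which allows a flexible number of looks.
- *That the ISM's freedom not to stop inflates the error.* Declining to stop after a crossing does not raise type I error.
- *That the target sample size is truly open between 126 and 147.* Section 9.4.7 gives no number, but 147 is the total in section 9.2, the synopsis and section 5.5, and is the natural reading. One confirming phrase is enough.
- *That the sample size is wrong.* It reproduces on its own inputs.

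**Conclusion.** The point holds as a fault of wording and consistency in a rule that the trial relies on. Section 9.4.7 is wrong as written in two places, and section 9.4.1 conflicts with it on the final primary test. It does not follow that the trial will run above 5%; that depends on which section the analyst follows.

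Under section 9.4.7 carried through, the error is 5.0%. Under section 9.4.1 it is about 5.1-5.7% with O'Brien-Fleming-type spending at 0.025 per side, up to 6.0% with 0.05 entered directly, and 6.9-7.5% with Pocock-type. These figures rest on the assumed schedule of one to four equally spaced interims, and the plan mentions neither family. The unnamed function is mainly missing detail, but it moves the first bound tenfold, and the 5% guarantee needs it to be chosen before outcomes are seen by group. This should be fixed; the likely inflation is modest.

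**What to change.** In section 9.4.7:

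1. Replace the reference to power with an overall two-sided type I error of 0.05.
2. State that the efficacy boundary is crossed when the primary-endpoint p-value is at or below the adjusted bound.
3. Name one spending function before any look at outcomes by group, for example Lan-DeMets O'Brien-Fleming-type, and say whether it is applied at 0.025 per side.
4. Confirm 147 as the target sample size.
5. Compute the final bound from the alpha remaining and the information actually observed, not from a fixed level.
6. State whether safety review uses this alpha. The trigger names safety next to primary efficacy, while section 9.1 lists safety as secondary. The choice is the sponsor's.

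In section 9.4.1, except the primary endpoint, whose final level is the one left by section 9.4.7. Looks at 49 and 98 of 147 would leave 0.0463 for a 1-df contrast or 0.0459 for the three-arm test, as an illustration.

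The cost is wording in two sections. With O'Brien-Fleming-type spending and two interims, the loss of fixed-sample power is at most about one percentage point at either N (working, step 5). Pocock-type spending would cost far more: at its final level of 0.0208 (2 df, same looks), power is 68.6% at N = 126 and 76.8% at N = 147.
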